9.7.4 Validation of Self-Reported Anti-Migraine Medication Use

Approximately 60% of participants will be randomly selected in each group (up to 600 in each treatment group) to describe the agreement between self-reported anti-migraine medication use and pharmacy claims records for all acute and preventive prescription anti-migraine medications at baseline and after 12 months of follow-up.

Pharmacy claims records will be reviewed and the consistency with self-reported medication use reported descriptively with relevant agreement statistics such as percentage of agreement, percentage of disagreement, Kappa statistics (Cohen, Fleiss or Weighted depending on the distribution of the class variable).

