9.3.3 Variables Collected at Baseline

In addition to the variables collected to identify eligible participants, and to create HRS profile, the following variables collected at baseline will be used to describe the recruited population as part of the primary study objective:

Participant characteristics

- Highest level of education, and
- Current employment status.

Migraine experience and use of anti-migraine medication

• Age at migraine diagnosis (calculated from self-reported date of migraine diagnosis),
- Migraine experience (i.e., over the past 12 months: presence of aura, average number of attacks per month, impact of migraine on daily life; over the past 30 days: number of attacks, impact of migraine on daily life),
- Use of acute and preventive prescribed anti-migraine medications over the past 12 months (medications names and dosage for lasmiditan), and
- Use of acute and preventive prescribed anti-migraine medications over the past 30 days (medications names and dosage for lasmiditan).

Medical history & concomitant medication use

- Relevant comorbidities at baseline (including hypertension, hypotension, musculoskeletal diseases, ophthalmological diseases, insomnia, anxiety, diabetes, depression, other psychiatric disease, chronic insomnia, chronic fatigue syndrome, seizure disorders), and
- Use of concomitant medications potentially associated with MVA risk (including antihistamines, antidepressants, benzodiazepines, beta-blockers, opioids, anti-seizure medications, antipsychotics, sleeping pills including sedatives and hypnotics) within the past 12 months and the past 30 days.

Driving characteristics and experience of MVAs for which the participant was the driver

- Type of active driver's licence,
- Approximate number of miles driven within the last year and in the past 30 days, and
- Self-reported MVAs for which the participant was the driver within the last 30 days and the last 12 months, details on the accident (including location of the accident, speed, perceived level of fault, time of the day, other vehicle(s) and/or persons involved, injuries, severity of the accident approximated by motor vehicle and property damages) and circumstances of these MVAs (details provided below).

Circumstances of self-reported MVAs for which the participant was the driver

- Migraine status at the time of MVA,

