9.4.3 ExamOne ScriptCheck Prescription Claims

ExamOne ScriptCheck is a data retrieval service utilised to verify participant pharmacy prescriptions and prescribed drug and dosage by providing the participant's last name, first name, sex, date of birth, phone number and residential address. Data is drawn from some of the largest pharmacy benefits management companies in the US, as well as self-pay data sources, and is anticipated to yield prescription claims data on the majority of study participants. ExamOne database covers about 93% of the US population and, when matches are obtained based on patient identifiers described above, has a match accuracy >99.8%.

ExamOne ScriptCheck prescription claims data on anti-migraine medications (preventive and acute) will be extracted for up to 60% of participants randomly selected in each treatment group (up to 600 participants in each treatment group) and will be linked to study data (see Annex 3). These prescription claims will be compared to self-reported anti-migraine medication use as described in Section 9.7.4. For each randomly selected participant, the data agreement will be assessed at 2 time points: once at baseline, and once at the end of the online survey data collection period described above.

The data extraction and linkage will operationally be performed twice: following the recruitment of the last participant and following the completion of the last survey by the last study participant. Self-reported use of prescribed acute anti-migraine medication will be utilised to assign treatment exposure category. No treatment strategy re-classification is planned after ScriptCheck concordance is assessed. The data concordance agreement aims to answer secondary objective to describe the concordance between self-reported use of prescribed anti-migraine medication (acute and preventive) and prescription claims records among study treatment groups' participants (Lasmiditan Group, Other Acute Medication Group and No Acute Medication Group).

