9.9 Limitations of the Research Methods

9.9.1 Participant Recruitment

As with many online studies, participants' eligibility will be predominantly self-reported. Given the relatively high number of participants the study aims to recruit, this approach is preferred to requiring participants to give evidence of their condition and medication as part of study inclusion, which would be substantially more operationally complex and would likely reduce recruitment numbers. Prescriptions will be verified via ExamOne ScriptCheck in a data validation procedure for approximately 60% of participants randomly selected in each group (up to 600 in each group) to describe the consistency between this self-reported prescription data and pharmacy claims records. According to data shared by ScriptCheck, ScriptCheck covers most of the US population (around 93%) with a match accuracy of 99.8%. However, pharmacy claims records represent only

medication dispensed, not medication actually taken by an individual. Additionally, participants will be referred by their HCP, who will confirm the participant's self-reported diagnosis of migraine.

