Annex 3. Additional Information

List of prescribed anti-migraine medications

Medication Name	Drug Class	Classification
Lasmiditan (Reyvow)	Ditan	Acute
Ubrogepant (Ubrelvy)	CGRP antagonist / gepant	Acute
Rimegepant (Nurtec)	CGRP antagonist / gepant	Acute*
Zavegepant (Zavzpret)	CGRP antagonist / gepant	Acute
Almotriptan (Axert)	Triptan	Acute
Eletriptan (Relpax)	Triptan	Acute
Rizatriptan (Maxalt)	Triptan	Acute
Sumatriptan Succinate (Imitrex, Sumavel, Alsuma, Zembrace)	Triptan	Acute
Frovatriptan (Frova)	Triptan	Acute
Naratriptan (Amerge)	Triptan	Acute
Zolmitriptan (Zomig, Zomig ZMT)	Triptan	Acute
Sumatriptan / Naproxen (Treximet)	Triptan / NSAID	Acute
Diclofenac (Cambia, Cataflam, Zipsor, Zorvolex)	NSAID	Acute
Galcanezumab (Emgality)	CGRP antagonist	Preventive
Erenumab (Aimovig)	CGRP antagonist	Preventive
Eptinezumab (Vypepti)	CGRP antagonist	Preventive
Fremanezumab (Ajovy)	CGRP antagonist	Preventive
Atogepant (Qulipta)	CGRP antagonist / gepant	Preventive
Topiramate (Topamax, Trokendi XR, Qudexy XR)	Antiepileptic	Preventive
Valproate sodium (Depacon)	Antiepileptic	Preventive
Divalproex sodium (Depakote, Depakote ER)	Antiepileptic	Preventive
Nortriptyline (Pamelor)	Tricyclic antidepressant	Preventive
Venlafaxine, Venlafaxine XR (Effexor, Effexor XR)	Antidepressant/SSRI/SSNRI/ TCA	Preventive
Amitriptyline	Tricyclic antidepressant	Preventive
Metoprolol (Toprol XL, Lopressor)	Beta Blocker	Preventive
Propranolol (Inderal LA, Hemangeol, InnoPran XL)	Beta Blocker	Preventive
Timolol (Blocadren)	Beta Blocker	Preventive
Atenolol (Tenormin)	Beta Blocker	Preventive
Nadolol (Corgard)	Beta Blocker	Preventive
Frovatriptan (Frova)	Triptan	Preventive
Naratriptan (Amerge)	Triptan	Preventive
Zolmitriptan (Zomig, Zomig ZMT)	Triptan	Preventive
OnabotulinumtoxinA (Botox)	Neurotoxin	Preventive
Bisoprolol (Zebeta)	Cardioselective beta blocker	Preventive
Candesartan Cilextile (Atacand)	Angiotensin II receptor blocker (ARB)	Preventive
Metoclopramide (Reglan, Maxolon, Metozolv ODT, Gimoti)	Prokinetic agent/ antiemetic	Preventive
Prochlorperazine (Compazine, Compro)	Antipsychotic/ antiemetic	Preventive

* Although rimegepant may be used for both acute treatment of migraine attacks and preventively, for this study all participants who report use of rimegepant will be classified as using acute prescription anti-migraine medication, which will allow for all potential acute use of rimegepant to be captured.

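### The concordance check sets migraine-specific self-report against claims defined only by drug, so agreement for preventive medication can understate how accurate self-report is

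*Protocol*

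**What the plan says.** Section 9.3.3 asks about medication by purpose: "Use of acute and preventive prescribed anti-migraine medications over the past 30 days (medications names and dosage for lasmiditan". Section 9.3.4 repeats the question at each follow-up survey.

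The claims side is defined by drug. Section 9.4.3 states "ExamOne ScriptCheck prescription claims data on anti-migraine medications (preventive and acute) will be extracted for up to 60% of participants" and points to Annex 3 for the list. It describes the service as one "utilised to verify participant pharmacy prescriptions and prescribed drug and dosage". Indication is not mentioned.

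Section 9.7.4 compares the two "to describe the agreement between self-reported anti-migraine medication use and pharmacy claims records for all acute and preventive prescription anti-migraine medications", using "relevant agreement statistics such as percentage of agreement, percentage of disagreement, Kappa statistics". It gives no rule for a listed drug dispensed for another condition.

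The survey also records "Use of concomitant medications potentially associated with MVA risk (including antihistamines, antidepressants, benzodiazepines, beta-blockers, opioids, anti-seizure medications, antipsychotics" and further classes. Table 2 places this item under other medical history, apart from migraine medication. Section 9.3.3 also collects hypertension, depression, anxiety, seizure disorders and musculoskeletal disease as comorbidities.

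The stated limit on claims, in Section 9.9.1, is that they show "medication dispensed, not medication actually taken by an individual". Section 9.9.2 says the claims comparison will assess the validity of self-reported prescription medication. Section 9.2.3 treats self-reported preventive use as a potential confounder and says its agreement with claims will be assessed.

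**The concern.** The two sides of the comparison do not measure the same thing. Take a participant with hypertension who fills "Metoprolol (Toprol XL, Lopressor"), a beta-blocker on the preventive list, only for blood pressure. This participant can truthfully report no preventive migraine drug and tick beta-blockers as concomitant medication. The claims extract still shows an Annex 3 preventive. Read literally, Section 9.7.4 has a claim with no matching self-report, although nothing was misreported.

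The reading of the result is at stake. Low agreement for preventives would be taken as poor self-report and would cast doubt on a covariate that Section 9.2.3 intends to adjust for. If cardiovascular, psychiatric or seizure comorbidity differs between treatment groups, agreement could differ too, with no difference in reporting accuracy.

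On the acute list, diclofenac may do the same. Filled for a musculoskeletal condition, it could make a correctly classified member of the No Acute Medication Group look like an unreported acute user.

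**Working it through.** **The plan's own figure.** Validation subset per group: 0.60 × 1000 = 600. This reproduces.

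**Count of Annex 3 preventive rows, matched to the concomitant classes in Section 9.3.3.**

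| Class | Drugs | Rows |
|---|---|---|
| Beta-blockers | metoprolol, propranolol, timolol, atenolol, nadolol, bisoprolol | 6 |
| Antidepressants | nortriptyline, venlafaxine, amitriptyline | 3 |
| Antiepileptics | topiramate, valproate, divalproex | 3 |
| Antipsychotic | prochlorperazine | 1 |
| **Overlap** | | **13** |
| No overlap | 4 CGRP antibodies, atogepant, 3 triptans, onabotulinumtoxinA, candesartan, metoclopramide | 11 |
| **All preventive rows** | | **24** |

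13/24 = 54%. Candesartan (an angiotensin receptor blocker) and metoclopramide (an antiemetic) may raise the same problem, but the survey names no concomitant class for either.

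**Acute rows.** There are 13: lasmiditan, 3 gepants, 8 triptan products and diclofenac. Only diclofenac is open to the problem.

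**Illustration of size.** Assume perfect recall, complete claims and one pooled yes/no item. Let P be the share using a listed drug for migraine, and q the share of the rest who fill a listed drug only for another condition. Neither is in the documents.

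- Both yes: P
- Claim yes, self-report no: (1 − P)q
- Both no: (1 − P)(1 − q)
- Observed agreement: po = 1 − (1 − P)q
- Claim-positive share: c = P + (1 − P)q
- Chance agreement: pe = cP + (1 − c)(1 − P)
- kappa = (po − pe)/(1 − pe)

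Worked case, P = 0.20 and q = 0.20: po = 1 − 0.16 = 0.84; c = 0.36; pe = 0.072 + 0.512 = 0.584; kappa = 0.256/0.416 = 0.62. Spurious disagreements in 600 participants: 600 × 0.16 = 96.

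| P | q | Agreement | kappa | Spurious pairs per 600 |
|---|---|---|---|---|
| 0.10 | 0.20 | 82% | 0.44 | 108 |
| 0.20 | 0.05 | 96% | 0.88 | 24 |
| 0.20 | 0.10 | 92% | 0.78 | 48 |
| 0.20 | 0.20 | 84% | 0.62 | 96 |
| 0.20 | 0.30 | 76% | 0.48 | 144 |
| 0.30 | 0.05 | 96.5% | 0.92 | 21 |
| 0.30 | 0.10 | 93% | 0.84 | 42 |
| 0.30 | 0.20 | 86% | 0.71 | 84 |
| 0.30 | 0.30 | 79% | 0.58 | 126 |
| 0.50 | 0.20 | 90% | 0.80 | 60 |

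With indication known, or with only migraine-specific drugs, kappa under the same assumptions is 1.00 in every row.

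**The case against.** Section 9.7.4 does not define a match, the unit of comparison or the scoring of an unmatched claim, and the protocol leaves further analysis detail to the statistical analysis plan, which is not shown. A matching rule may exist there. This stands, so one cannot say that the plan definitely scores correct reports as errors. But the protocol itself fixes the comparison set as all listed drugs and the interpretation as validity of self-report. A plan that followed that text literally would produce the effect.

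The survey wording is also unseen. Section 9.3.3 calls the concomitant drugs potentially associated with accident risk, not drugs for conditions other than migraine, and nothing prevents a participant from naming a beta-blocker under both items. If drugs are offered by name, some participants may select them whatever the reason for use. The absence of indication from the claims is likewise inferred from the fields named. All of this could shrink the effect.

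A reader might infer that the study's exposure measurement, and with it the primary comparison, is undermined. The documents do not support that. All 13 overlapping drugs are preventives, and Section 9.1 excludes preventive use from group assignment. Twelve of the 13 acute rows are lasmiditan, gepants or triptan products. Section 9.4.3 rules out reclassification after the concordance check.

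**Conclusion.** The mismatch is real and follows from the protocol's own lists. Agreement for preventive medication can understate the validity of self-report, and the only limit stated for claims, dispensed versus taken, does not cover it.

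The size cannot be derived from the documents. The illustrative kappas of 0.44 to 0.92 rest on assumed shares, perfect recall, complete claims and a pooled any-listed-drug item; a per-drug comparison would give other values. They show only that the effect may be small or large.

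The consequence is confined to the secondary concordance objective and to the reading of preventive use as a confounder. Group assignment and the primary hazard ratio are not affected. The one link to acute exposure is diclofenac in the check of the No Acute Medication Group. The change is worth making before the analysis, but it does not threaten the main result.

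**What to change.** In Section 9.7.4, keep the all-drug agreement, report acute and preventive medication separately, and split each:

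- **(a) Drugs whose claim by itself points to migraine treatment:** lasmiditan, gepants, triptans and CGRP antibodies. Use this as the main validity figure.
- **(b) Drugs with other common uses:** beta-blockers, antidepressants, antiepileptics, prochlorperazine, candesartan, metoclopramide and diclofenac.

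For (b), show pairs with a claim but no anti-migraine self-report as their own category, subdivided by whether the matching concomitant class was reported. Candesartan, metoclopramide and diclofenac have no named class, so show theirs undivided. Give agreement twice, counting these pairs as discordant and as concordant. Do not simply score them as agreement: someone who takes propranolol for migraine, omits it there and ticks beta-blockers would then hide a real reporting error.

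Assign onabotulinumtoxinA to (a) or (b) in advance. State how claims for frovatriptan, naratriptan and zolmitriptan are allocated, since Annex 3 lists each as both acute and preventive and, unlike rimegepant, gives no rule.

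Add to Section 9.9.1 that the claims are not expected to show indication, or name the field if they do.

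Cost: wording, a little more programming on data already collected, and a main figure that covers fewer drugs.

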9.7.5 Validation of Self-Reported Diagnosis of Migraine

For participants enrolled in Phase 2 of the study, referring HCPs will confirm self-reported diagnosis of migraine. The agreement between self-reported migraine diagnosis and review of the medical records by referral HCPs will be assessed and reported descriptively with relevant agreement statistics such as percentage of agreement, percentage of disagreement, Kappa statistics (Cohen, Fleiss or Weighted depending on the distribution of the class variable). No participant will be withdrawn if the diagnosis of migraine is not confirmed by the referring HCP, but the information will be included in the concordance analyses and discussed as potential limitation.

9.8 Quality Control

A data management plan (see further details in Section 9.6) will be created before data collection begins and will describe all functions, processes, and specifications for data collection, cleaning, validation, and monitoring. Changes to data collection on the HRS data platform will require documentation of the reason for each change.

HRS will configure and test the survey functions and logic as part of the end-to-end participant experience of the platform. The platform configuration and development must be complete and tested following software development lifecycle processes before starting to enrol participants via the HRS platform for each of the three participant groups. HRS platform software development lifecycle process includes proctored user acceptance testing activities in addition to thorough software testing at all stages of platform configuration.

Data quality will be enhanced through a series of programmed data quality checks that automatically detect out-of-range or anomalous data and will prompt the participants to re-enter a valid response. Data fields in the online survey will be limited to reduce ineligible answers and there will be a very limited number of open data fields to maximise data quality. The online survey will also prevent multiple survey entries from the same participants. Participants will be required to complete all questions in the online survey. To reduce the opportunity for bias, online survey participants will not be contacted to clarify or revise their responses.

As the online survey invitations will be sent for 12 months for each participant, IQVIA will ensure the appropriate follow-up to maintain proper participant engagement and share status updates to Eli Lilly raising potential issues/concerns with appropriate mitigations.

9.9 Limitations of the Research Methods

9.9.1 Participant Recruitment

As with many online studies, participants' eligibility will be predominantly self-reported. Given the relatively high number of participants the study aims to recruit, this approach is preferred to requiring participants to give evidence of their condition and medication as part of study inclusion, which would be substantially more operationally complex and would likely reduce recruitment numbers. Prescriptions will be verified via ExamOne ScriptCheck in a data validation procedure for approximately 60% of participants randomly selected in each group (up to 600 in each group) to describe the consistency between this self-reported prescription data and pharmacy claims records. According to data shared by ScriptCheck, ScriptCheck covers most of the US population (around 93%) with a match accuracy of 99.8%. However, pharmacy claims records represent only

medication dispensed, not medication actually taken by an individual. Additionally, participants will be referred by their HCP, who will confirm the participant's self-reported diagnosis of migraine.

9.9.2 Information Bias

As with all collection of self-reported data, there is the possibility that participants may give inaccurate responses. For prescription anti-migraine medication, agreement between self-report and pharmaceutical claims data was notably higher when participants were asked to report 'current' use (kappa statistic 0.66, 95% confidence interval [CI] 0.23-1.00) relative to the results for a recall period of the past year (kappa statistic 0.36, 95% confidence interval [CI] 0.00-0.72). (Lacasse et al. 2016) Validation with pharmacy claims data will assess the internal data validity of self-reported prescription medication.

Sensitive data regarding MVAs are being collected in the study, including whether the accident was reported, the use of medications, drugs, or alcohol prior to the accident, and/or distracted driving, which could predispose participants to not answer truthfully due to the fear of judgment or embarrassment. For MVAs, there is evidence that self-reported data has poor test re-test reliability. (af Wåhlberg and Dorn 2015) The risk of social desirability bias may be mitigated by use of an anonymised online survey, combined with assurance on data privacy, compared to interview-based methods. This will be emphasised in the survey instructions to encourage accurate and truthful responses from participants. Moreover, participants will not be able to change answers once they are submitted and will not be contacted to clarify or revise responses at any point. If a participant reports illegal activities (i.e., taking illegal drugs or taking medications that are not allowed before driving), he will be aware that no action will be taken.

The survey will ask participants to consider their driving and migraine experience within the last 30 days and within the last 12 months at baseline; while the primary analysis depends on the relatively recent 30-day period, there remains the potential for recall bias, particularly for self-reported data within the last 12 months. In case of a collision, the longer the time elapsed since the collision, the more difficult it will be for the participants to recall. This may have an impact on their ability to accurately report circumstances and events occurring the hours proceeding the accident (e.g., accurately recall the timing of any accidents relative to when medications were last taken). To minimise recall bias in this study, participants will be administered follow-up surveys every 30 days, will be instructed to complete a survey in one sitting and guided to answer the questions in sequence. The questionnaires have been designed to collect only the information required for the analytic objectives to minimise recall burden. At baseline, a limited set of key variables will be collected for MVAs within the past 12 months to limit the burden on participants and improve response accuracy, and results for the 12-month period will be interpreted cautiously.

Because treatment and outcome variables are ascertained at the 30-day level, temporality between treatments and outcomes reported in the same interval cannot be established. For this reason, the primary statistical analysis is designed to estimate the hazard of experiencing a MVA in the *subsequent time interval* given treatment history *in the time interval prior* to the MVA. If a participant had in fact ceased using the treatment reported in the interval prior to the MVA, or begun an alternate treatment in the interval in which the accident was reported, then the participant's treatment status maybe misclassified. However, this misclassification bias is likely to be non-directional, resulting in a similar bias on the effect estimation between treatment groups.

Secondary objectives were specified to investigate the extent of treatment misclassification for this cause providing additional information on circumstances of MVA, including use of anti-migraine medication in the 24 hours prior to the accident.

